2.1.2 Exclusion Criteria

- 2.1.2.1 Patients who are receiving any other investigational agents. However, prior enrollment on a study using investigational agents is acceptable as per section [2.1.1.12](#).
- 2.1.2.2 Patients with prior bevacizumab use for tumor treatment. Patients who received bevacizumab for symptom management, including but not limited to cerebral edema, pseudo progression can be included in the study. (To date, there have been no effective regimens developed for recurrent malignant gliomas that are refractory to bevacizumab. Inclusion of this patient population may impact the ability to determine the efficacy of Zotiraciclib [TG02] with TMZ.)
- 2.1.2.3 Any serious medical condition, laboratory abnormality, or psychiatric illness that would prevent the subject from providing informed consent.
- 2.1.2.4 Any condition, including the presence of clinically significant laboratory abnormalities, which places the patient at unacceptable risk if he/she were to participate in the study or confounds the ability to interpret data from the study. These would include:
 - 2.1.2.4.1 Active infection (including persistent fever) including known history of HIV or Hepatitis C infection, because these patients are at increased risk of lethal infections when treated with marrow-suppressive therapy.
 - 2.1.2.4.2 Diseases or conditions that obscure toxicity or dangerously alter drug metabolism.
 - 2.1.2.4.3 Serious concurrent medical illness (e.g. symptomatic congestive heart failure).

- 2.1.2.5 History of allergic reactions attributed to compounds of similar chemical or biologic composition to temozolomide and/or Zotiraciclib (TG02).
- 2.1.2.6 Patients with a history of any other cancer (except non-melanoma skin cancer; or melanoma in-situ following curative surgical resection; or carcinoma in-situ of the cervix or bladder), unless in complete remission and off all therapy for that disease for a minimum of 3 years, are ineligible.
- 2.1.2.7 Zotiraciclib (TG02) is primarily metabolized by CYP1A2 and CYP3A4. Patients receiving any medications or substances that are strong inhibitors or inducers of *CYP1A2 and/or CYP3A4* are ineligible. Lists including medications and substances known or with the potential to interact with the CYP1A2 and CYP3A4 isoenzymes are provided in [15.3](#).
- 2.1.2.8 Patients, who continue to have prolonged QTc (males: >450ms; females: >470ms as calculated by Fridericia's correction formula) despite normal electrolyte balance and discontinuation of medications known to prolong QTc, will be excluded from the study.

2.1.3 Recruitment Strategies

This protocol may be abstracted into a plain language announcement posted on NIH websites and on NIH social media platforms.

2.2 SCREENING EVALUATION

2.2.1 Screening activities performed prior to obtaining informed consent

Minimal risk activities that may be performed before the subject has signed a consent include the following:

- Email, written, in person or telephone communications with prospective subjects
- Review of existing medical records to include H&P, laboratory studies, etc.
- Review of existing MRI, x-ray, or CT images
- Review of existing photographs or videos
- Review of existing pathology specimens/reports from a specimen obtained for diagnostic purposes

A waiver of consent for these activities has been requested in section [12.6.1](#).

2.2.2 Screening activities performed after a consent for screening has been signed

The following activities will be performed only after the subject has signed the study consent OR the consent for study 01-C-0129 (provided the procedure is permitted on that study) on which screening activities may also be performed. Assessments performed at outside facilities or on another NIH protocol within the timeframes below may also be used to determine eligibility once a patient has signed the consent.

To be completed within 14 days of study registration, unless otherwise indicated

- 2.2.3 Unstained paraffin tissue from surgical samples will be obtained. A representative paraffin tissue block (at least 5 mm x 5 mm) or unstained slides will be obtained from previous surgery to confirm the histological diagnosis and molecular markers before entry into the clinical trial.
- 2.2.4 All patients with recurrent anaplastic astrocytoma or glioblastoma/gliosarcoma will need to have confirmation of pathology diagnosis on initial disease or recurrent disease, by a Neuropathologist at the NIH. The recurrent status of the disease must be confirmed by either by pathology diagnosis on tissue from recurrent disease or by imaging review by the PI. Confirmation of pathology diagnosis may occur any time prior to study entry.
- 2.2.5 A Gd-DPTA enhanced MRI, with DWI, ADC, SWI, FLAIR, perfusion, dynamic contrast enhanced, and dynamic susceptibility contrast sequences is needed within 14 days of entry into the study in all patients without surgical resection to establish the diagnosis of recurrent disease. The treating physician will review the Gd-DPTA MRI scan done prior to study entry documenting progression, if no tumor tissue available for pathology diagnosis.
- 2.2.6 Complete history and physical exam completed by principal or associate investigator, including thorough documentation of signs and symptoms caused by the tumor, determination of KPS, neurological function and mental status.
- 2.2.7 Screening laboratory tests will include CBC, differential, platelets, PT, PTT, INR, total protein, albumin, calcium, phosphorus, magnesium, glucose, BUN, creatinine, sodium, potassium, total bilirubin, alkaline phosphatase, LDH, SGPT (ALT), SGOT (AST), 12-lead EKG and a pregnancy test for women of child bearing potential.

2.3 PARTICIPANT REGISTRATION AND STUDY STATUS UPDATE PROCEDURES

Registration and status updates (e.g. when a participant is taken off protocol therapy and when a participant is taken off-study) will take place per CCR SOP ADCR-2, CCR Participant Registration & Status Updates found [here](#).

Patients must initiate study treatment within 7 calendar days after registration.

2.3.1 Treatment Assignment and/or Randomization/ Stratification Procedures*

Cohorts

Number	Name	Description
1	Cohort 1	Patients with recurrent anaplastic astrocytoma or glioblastoma/gliosarcoma assigned to Phase 1

2	Cohort 2	Patients with recurrent anaplastic astrocytoma or glioblastoma/gliosarcoma assigned to Phase 2
---	----------	--

Arms

Number	Name	Description
1	Phase I Arm 1	dose dense TMZ+ Zotiraciclib (TG02)
2	Phase I Arm 2	metronomic TMZ+ Zotiraciclib (TG02)
3	Phase II Arm 1	TMZ + Zotiraciclib (TG02)
4	Phase II Arm 2	TMZ (Control Arm)

Stratifications

Name	Distinct Options
KPS	Yes No
MGMT promoter methylation status of the tumor	Yes No
Presence of Measurable Disease	Yes No

In Phase I, study patients will be assigned to one of two arms to receive Zotiraciclib (TG02) plus dd TMZ or Zotiraciclib (TG02) plus mn TMZ in 1:1 ratio*. Once a phase II dose/schedule is determined, patients will be randomized to the following arms in 1:1 ratio - Zotiraciclib (TG02) plus TMZ (dose and schedule selected from phase 1 component) or Control Arm – TMZ (dosing schedule will match combination arm). Patients’ KPS, MGMT promoter methylation status of the tumors and the presence of measurable disease at study entry will be used as stratification factors.

*In Phase I, Post-interim analysis patients will be registered to cohort 1 and assigned to ARM 1, at a TG02 dose level of 200mg. Patients will be enrolled consecutively to cohort 1. Details are described in Section [3.2.1.3](#).

2.4 BASELINE EVALUATION

Baseline tests do not need to be repeated if the same tests were done within 14 days of treatment initiation.

- 2.4.1 A complete history and physical (including baseline blood pressure measurement) and neurological examination (include documentation of the patients' height, weight and Karnofsky Performance Status), as well as documentation of measurable and/or evaluable disease shall be performed on all patients.
- 2.4.2 A baseline Gd-DPTA enhanced MRI, with DWI, ADC, SWI, FLAIR, perfusion, dynamic contrast enhanced and dynamic susceptibility contrast sequences should be performed. The baseline on-study MRI should be performed on a steroid dosage that has been stable or decreasing for at least 5 days. If the steroid dose was increased between the date of imaging and the initiation of therapy (or at that time), a new baseline MRI is required. MRI study needs to be done within 14 days of the initiation of the study treatment.
- 2.4.3 Pre-treatment laboratory tests will include CBC, differential, platelets, PT, PTT, INR, total protein, albumin, calcium, phosphorus, magnesium, glucose, BUN, creatinine, sodium, potassium, total bilirubin, alkaline phosphatase, LDH, SGPT (ALT), SGOT (AST), 12-lead EKG and a pregnancy test for women of child bearing potential. Blood tests must be performed within 14 days (+ 3 working days) of registration, with day 0 = registration date. Pregnancy test must be obtained 14 days (+ 3 working days) before treatment starts.
- 2.4.4 Patients will complete a baseline MD Anderson Symptom Inventory-Brain Tumor Module (MDASI-BT) (**Error! Reference source not found.**). The MDASI-BT will only be completed by the patient, unless changes in vision or weakness make this difficult. If this occurs, then the caregiver or research assistant may read the questions to the patient or assist with marking the severity number or score as described by the patient. A patient caregiver may complete the questionnaires as a patient-preference proxy if the patient's deficits preclude self-report. If the MDASI-BT is completed by the patient for Natural History study, 16C0151 within (+/-) 14 days from the initiation of the treatment, then it can be used as the baseline.
- 2.4.5 Rapid clinical deterioration from the time of study entry to initiation of treatment will mandate a full re-evaluation including physical examination, KPS, MRI, and laboratory studies including CBC and blood chemistries and MDASI as outlined in Sections [2.5.1](#) - [2.4.4](#).

3 STUDY IMPLEMENTATION

3.1 STUDY DESIGN:

3.1.1 Phase I:

The phase I component is designed to find the MTD of Zotiraciclib (TG02) in combination with 2 schedules of TMZ – dose dense and metronomic. Patients will be enrolled and equally assigned into the two dosing schedule arms for MTD finding. In each arm, the MTD will be determined independently using the Bayesian Optimal Interval (BOIN) design, fully described in Section 8 and recently published [45]. Once the MTDs of the two regimens (dd TMZ + Zotiraciclib (TG02) and mn TMZ + Zotiraciclib [TG02]) have been established, cohort expansion will be carried out at the each of the MTDs. Patients will be equally randomized into to the two cohort expansions. A post interim analysis cohort will be carried out in cohort 1 arm 1 to confirm MTD. The MTD that has higher progression-free survival rate at 4 months (PFS4) will be selected and used in phase II.

3.1.2 Phase II:

The two-arm randomized phase II will determine if the addition of Zotiraciclib (TG02) to the dd or mn TMZ schedule (determined by the expanded phase I) improves outcome in patients with recurrent malignant glioma using PFS as the primary outcomes measure. Patients will be equally randomized into the combination Arm (Zotiraciclib [TG02] plus TMZ selected from phase I) and control arm (TMZ). The randomization will stratify by the presence of measurable disease at the study entry, KPS and MGMT promoter methylation status. Additional outcomes such as PFS6, overall survival from study entry and symptom burden (using the MDASI-BT instrument in Appendix **Error! Reference source not found.**) will also be collected.

The study schema is illustrated in Study Flow Chart in Appendix 15.4.

3.1.3 Definition of dose limiting toxicities (DLT)

All patients in the MTD finding phase of the phase I part will be evaluable for assessment of toxicity to define DLTs. The DLT-defining period is the first 4 weeks' treatment in the Phase I study.

Toxicities will be graded per the Common Terminology Criteria for Adverse events (CTCAE) Version 4.0. If multiple toxicities are seen, the presence of DLT should be based on the most severe toxicity experienced. DLT is defined as any of the following events occurring in the first cycle of treatment (4 weeks) and attributable to the study drugs:

- Any of the following hematological toxicities:
 - Grade 4 neutropenia lasting 5 days or more.
 - Febrile neutropenia defined as grade 3-4 neutropenia with fever $\geq 38.5^{\circ}\text{C}$ and/or infection requiring antibiotic or antifungal treatment.
 - Grade 4 thrombocytopenia lasting more than 2 days.
 - Grade 3 thrombocytopenia with bleeding of any duration

- Grade 3 or 4 anemia lasting more than 2 days.
- Any non-hematologic grade 3 or 4 toxicity, except the following
 - nausea or vomiting that responds to symptomatic therapy and lasts ≤ 7 days.
 - Diarrhea that responds to symptomatic therapy within 2 days.
 - fatigue that responds to symptomatic therapy and lasts ≤ 7 days.
 - weight gain (in patients on steroids)
 - venous thromboembolic disease (rationale for not including this event as a DLT described below)
- If there is a dose reduction of either or both study medications or if a dose is held or discontinued in cycle 1, this constitutes a DLT, per PI discretion.
- Grade 4 lymphopenia is not considered as a DLT for this study. All patients for this study have treated with alkylating agents and radiation treatment. Lymphopenia can be highly associated with the previous treatment or have a low threshold to have severe lymphopenia because of the previous treatments. In case of isolated laboratory abnormalities that may not reach clinical significance, a determination will be made by PI or in consultation with the IRB on a case-by-case basis to determine if DLT needs to be declared.
- Failure to recover from treatment related toxicities to be eligible for re-treatment within 4 weeks of the last dose of the drugs.

3.2 DRUG ADMINISTRATION

3.2.1 Phase I treatment

3.2.1.1 Drug dosage

There are two treatment arms in this component: the combination treatment of Zotiraciclib (TG02) and dd TMZ; and the combination treatment of Zotiraciclib (TG02) with mn TMZ. In both treatment arms, several dose levels are planned as outlined in section 3.1.4. The starting dose of Zotiraciclib (TG02) is 200 mg/day orally on days 1, 12, 15, and 26 on a 28-days cycle in both treatment arms, except for that the first dose of Zotiraciclib (TG02) will be given 3 days prior to Day1 in cycle 1. The dosing schedule for both treatment arms are illustrated in the Appendix 15.6. TMZ is administered at 125mg/m² daily on days 1-7 and 15-21 orally in dd TMZ schedule and 50mg/m² daily in mn TMZ schedule. The dosing schedule was designed with the intention to avoid potential overlapping toxicity from both drugs. The proposed dosing schedule will allow patients have less chance to have to take both medications on the same day. Based on our preclinical data that Zotiraciclib (TG02) reduces expression of anti-apoptotic protein and better anti-glioma effects with pretreatment of Zotiraciclib (TG02) and followed by combination treatment, one dose of Zotiraciclib (TG02) will be administered 3 days prior to first dose of TMZ in the first cycle. In the subsequent cycles, the doses that patients receive on day 26 would be the exactly 3 days prior to TMZ administration on day 1 of the following cycles. We will employ the Bayesian optimal interval (BOIN) design [46] to guide dose escalation and find the MTD. The details of the design are provided in Section 8.

3.2.1.2 Cohort expansion:

After identifying the MTD for each of the TMZ dosing schedules in combination with Zotiraciclib (TG02) (i.e., 125mg/m² TMZ on days 1-7 and 15-21 per cycle, and 50 mg/m² TMZ daily), cohort expansion will be conducted independently at each of the MTDs until the total number of patients treated at each of the MTDs reaches 18 patients (including the patients who have been treated in the dose-finding part). The dosing schedule with a higher PFS4 will be selected and used in phase II.

3.2.1.3 Post interim analysis cohort:

Patients will be enrolled to Arm 1 only to receive Zotiraciclib (at Dose level 0 and in combination of dd TMZ). TG02 dose is 200 mg/day orally on days 1, 12, 15, and 26 on a 28-days cycle, except for that the first dose of Zotiraciclib (TG02) will be given 3 days prior to Day1 in cycle 1. TMZ is administered at 125mg/m² daily on days 1-7 and 15-21 orally on a 28-days cycle.

3.2.2 Phase II treatment:

The combination treatment selected from phase I (with better PFS4) will be tested against the TMZ alone with the same dosing schedule as it is in the combination arm. Patients will be randomized on a 1:1 basis between two competing treatment arms: TMZ + Zotiraciclib (TG02) versus TMZ alone using a Bayesian phase II trial design. The details of the design are provided in Section 8.

The dosage for the combination arm is derived from the MTD of the combination determined in the phase I component of the study. The treatment schedule will be identical to that described above in the phase I component, with each cycle comprising 28 days.

Patients will continue treatment until tumor progression or unacceptable toxicity occurs or completion of 12 cycles of treatment. At progression, patients randomized to the control arm (TMZ alone) will be offered the opportunity to continue TMZ and the additional treatment with Zotiraciclib (TG02). After administration of 12 cycles of treatment, patients may stay on the study treatment, if there is evidence of clinical benefit based on treating physician's discretion.

If patient vomits Zotiraciclib (TG02), do not re-administer.

3.3 DOSE MODIFICATION/DELAYS:

If an adverse event occurs wherein both TMZ and Zotiraciclib (TG02) would require dose de-escalation, the Principal Investigator shall have the discretion of first dose reducing one of the 2 study drugs with the consideration of previously known drug toxicities/side effects in an effort to further define attribution.

Table 8: Start of Each Cycle for both TMZ and Zotiraciclib (TG02)		
Temozolomide and Zotiraciclib (TG02)		
Hematologic*	ANC $\geq 1.5 \times 10^9/L$ and PLT $\geq 100 \times 10^9/L$	No dose modification
	ANC $< 1.5 \times 10^9/L$ and/or Platelet count $< 100 \times 10^9/L$	Delay up to 4 weeks until ANC $\geq 1.5 \times 10^9/L$ and PLT $\geq 100 \times 10^9/L$. If unresolved after 4 weeks, then stop. If resolved, dose delay/reductions based on Table 9.
Non-Hematologic	Grade 1 or less	No dose modification
	Grade 2	Zotiraciclib (TG02): Delay up to 4 weeks until \leq Grade 1. If unresolved after 4 weeks, then dose reduce by 1 dose level. Temozolomide: dose delay/reductions based on Table 9, if adverse event attributed to Temozolomide.
	Grade 3	Zotiraciclib (TG02): Delay up to 4 weeks until \leq Grade 1. If unresolved after 4 weeks, then stop. If resolved to \leq Grade 1, then dose reduce by 1 dose level. Temozolomide: dose delay/reductions based on Table 9, if adverse event attributed to Temozolomide.
	Grade 4	Discontinue treatment

*With the exception of lymphopenia, grade 1-4. Patient may start a cycle with G2 WBC, as long as the ANC $\geq 1.5 \times 10^9/L$.

3.3.1 Temozolomide (TMZ) Dose Modifications

Dose modification(s) are based on adverse event occurrence and may be implemented during any treatment cycle (Table 11) or prior to initiation of each new cycle per Table 8. If multiple AEs are seen, the dose administered should be based on the dose reduction required for the most severe grade of any single AE. If TMZ is delayed or discontinued in combination therapy, the Zotiraciclib (TG02) component of treatment may continue, unless there is clear reason to discontinue Zotiraciclib (TG02) simultaneously.

Table 9: TMZ Dose Levels for Modification Table		
Dose Level	DD TMZ Dose, mg/m²/day	MN TMZ Dose, mg/m²/day
-2	80	32
-1	100	40
0	125	50

3.3.1.1 Delay

For treatment on day 1 of each cycle (within the prior 72 hours), ANC $\geq 1.5 \times 10^9/L$, platelet count $\geq 100 \times 10^9/L$ and all grade 2 -3 non-hematologic AEs (except nausea and vomiting) must have resolved (to grade ≤ 1). For grade 4, discontinue treatment. For the purposes of this study, any clinically insignificant Grade 2 or 3 electrolyte abnormalities with attribution of unlikely related to or unrelated to study medications, will not require holding or dose-reducing study medications.

If AEs persist, treatment may be delayed by 1 week for up to 4 consecutive weeks. If, after 4 weeks of delay, all AEs have still not resolved to grade 1 or less: then any further treatment with temozolomide should be stopped, as summarized in Table 8 and Table 11.

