Table 10: Zotiraciclib (TG 02) Dose Modification Table	
Dose Level	TG 02 (mg/day on days 1, 12, 15, 26 per 28 day cycle)*
-1	150
0	200
1	250
2	300

Summary of Dose Modification or Discontinuation

Table 11: Dose Modifications and Delay*				
	Zotiraciclib (TG02)		TMZ	
Grade	Hematologic**	Non-hematologic	Hematologic**	Non-hematologic
0-1	No dose modification	No dose modification	No dose modification	No dose modification

Table 11: Dose Modifications and Delay*				
	Zotiraciclib (TG02)		TMZ	
2	Hold until resolved to ≤ G1; if persists beyond 4 weeks, dose reduce one level.	Hold until resolved to ≤ grade 1; if > 4 weeks then dose reduce 1 level.	Hold until resolved to ≤ grade 1; if > 4 weeks then dose reduce 1 level.	No dose modifications for non-hematologic AEs (G 0-2), unless the adverse event attributed to Temozolomide.
3	If not recovered to ≤ G2 within 3 days, STOP. If recovered to ≤ G2 within 3 days, re-start @ one dose level lower once recovered to G1 or less.***	Delay up to 4 weeks until ≤ Grade 1. If unresolved after 4 weeks, then stop. If resolved to ≤ grade 1; then dose reduce by 1 level.	Hold until resolved to ≤ grade 1; if > 4 weeks, then stop.	Hold until resolved to ≤ grade 2; if greater than 4 weeks then stop. If less than 4 weeks, reduce by one dose level. If the same non-hematologic grade 3 AE recurs after reduction for that AE, then stop.
4	If not recovered to ≤ G2 within 3 days, STOP. If recovered to ≤ G2 within 3 days, re-start @ one dose level lower once recovered to G1 or less	Stop treatment.	Stop treatment.	Stop treatment.

* If the patient develops a lower extremity deep venous thrombosis and requires anticoagulation or intervention (grade 2 or 3 toxicity), treatment may be restarted after a 2-week rest period if the patient is stably anticoagulated and is judged medically stable to begin chemotherapy. (Please note: DVT is graded in the CTC version 4.0 as grade 1= superficial thrombosis, grade 2= DVT, medical intervention indicated, grade 3= uncomplicated pulmonary embolism, medical intervention indicated, grade 4=life-threatening pulmonary embolism, cerebrovascular event, arterial insufficiency, urgent intervention indicated).

** With the exception of lymphopenia, grade 1-4.

***If G3 neutropenia recovers within 72 hours, the Principal Investigator may consider no dose reduction of Zotiraciclib (TG02).

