3.10 CRITERIA FOR REMOVAL FROM PROTOCOL THERAPY AND OFF STUDY CRITERIA

3.10.1 Criteria for Removal from Protocol Therapy

- After administration of 12 cycles of treatment, unless there is clear evidence of clinical benefit to justify continuation of treatment based on treating physician's opinion.
- Progressive disease if patient not eligible for or refuses crossover or progressive disease * after crossover to TMZ+ Zotiraciclib (TG02)
- The patient may withdraw from the study at any time for any reason
- Unacceptable Toxicity as defined in section **3.3**
- Investigator discretion
- Treatment related adverse events not resolved within a 4-weeks rest period or requiring more than two dose de-escalations of any drug whichever is earlier.
- Pregnancy

* Delayed imaging responses have been observed in some patients who received protocol treatment. If a patient is clinically stable or clinically improved, even while MRI showed >25% increase in tumor size, the patient may continue on study treatment per P.I. discretion for one additional cycle, at which time a repeat scan will be done. If tumor size continues to increase, disease progression will be dated back to the date of prior MRI.

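### For a treatment-related grade 2 toxicity unresolved after 4 weeks, section 3.10.1 ends protocol therapy, but grade 2 cells in Tables 8 and 11 reduce the dose and continue

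*Combined protocol and SAP*

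**What the plan says.** The general removal rule in 3.10.1 lists: "Treatment related adverse events not resolved within a 4-weeks rest period or requiring more than two dose de-escalations of any drug whichever is earlier". It carries no grade limit.

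For temozolomide, 3.3.1.1 deals with dosing on day 1 of each cycle. It allows postponement: "If AEs persist, treatment may be delayed by 1 week for up to 4 consecutive weeks". If events are still above grade 1 after that, "then any further treatment with temozolomide should be stopped, as summarized in Table 8 and Table 11".

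The tables give these grade 2 instructions:

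- Table 8, zotiraciclib, non-hematologic: "If unresolved after 4 weeks, then dose reduce by 1 dose level".
- Table 11, zotiraciclib, hematologic: "Hold until resolved to ≤ G1; if persists beyond 4 weeks, dose reduce one level".
- Table 11, zotiraciclib non-hematologic and temozolomide hematologic, in the same words: "Hold until resolved to ≤ grade 1; if > 4 weeks then dose reduce 1 level".

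Where the tables mean stop, they say so. The Table 11 cell for temozolomide hematologic grade 3 reads "Hold until resolved to ≤ grade 1; if > 4 weeks, then stop". Table 8's hematologic row, which covers both drugs and works on neutrophil and platelet thresholds rather than grades, also stops after 4 unresolved weeks.

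Section 3.3.2 adds a further statement for zotiraciclib: the dose stays the same unless drug-related toxicity reaches grade 3 or higher.

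**The concern.** Whether a patient with slow-resolving toxicity receives the drug again at a lower dose or leaves protocol therapy is a safety decision. For grade 2 events the protocol gives both answers and does not say which text prevails. Two investigators could each follow the protocol and act in opposite ways, and a monitor could not say which of them had deviated. The 3.3.2 sentence adds to the problem: read literally, it leaves the zotiraciclib dose unchanged for grade 2 events, which fits neither stopping nor reducing.

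**Working it through.** No power or error-rate calculation applies. The check sets the instructions side by side.

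**Step 1. Count the cells in Tables 8 and 11 that state what happens at 4 weeks.**

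- Stop (5): Table 8 hematologic row; Table 8 zotiraciclib non-hematologic grade 3; Table 11 zotiraciclib non-hematologic grade 3; Table 11 temozolomide hematologic grade 3; Table 11 temozolomide non-hematologic grade 3.
- Reduce (4): Table 8 zotiraciclib non-hematologic grade 2; Table 11 zotiraciclib hematologic grade 2; Table 11 zotiraciclib non-hematologic grade 2; Table 11 temozolomide hematologic grade 2.

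5 + 4 = 9. All four reducing cells are grade 2.

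**Step 2. Compare the four reducing cells with 3.10.1, for a treatment-related event.**

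- In Table 8's zotiraciclib cell and Table 11's zotiraciclib hematologic cell, the trigger for reduction is that the toxicity is still present past 4 weeks. That is the condition on which 3.10.1 ends therapy.
- The other two cells hold until grade 1 or less and reduce if this takes more than 4 weeks. They can mean resuming one level lower after a late recovery. Whether that conflicts with 3.10.1 depends on when its 4 weeks start.

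**Step 3. Look at the clock.** The text uses three expressions: a delay of day 1 treatment (3.3.1.1), a rest period with no stated start (3.10.1) and, for DLT only, time since the last dose (3.1.3: "Failure to recover from treatment related toxicities to be eligible for re-treatment within 4 weeks of the last dose of the drugs"). Let d be the cycle day of the first held dose, and assume that the next planned day 1 stays at day 29.

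- Four weeks from the first held dose end on day d + 28.
- Four weeks of delay from the next day 1 end on day 29 + 28 = 57.
- The gap is 57 − (d + 28) = 29 − d days.

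Example: dose-dense temozolomide first held on day 15. The two end points are day 43 and day 57, which are 14 days apart. Suppose counts recover on day 50. Table 11 would then resume one level lower. On the first-held-dose clock, 3.10.1 already ended therapy on day 43, so the two conflict. On the day 1 delay clock, 3.10.1 has not yet been triggered, so they do not.

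**Step 4. Compare the temozolomide cell with 3.3.1.1.** That section stops temozolomide after 4 unresolved weeks and cites both tables as its summary. Table 8's hematologic row agrees. Table 11's temozolomide hematologic grade 2 cell gives only a reduction and never a stop, so it does not summarize the rule.

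**Step 5. Look for a rule of precedence.** None is stated. In 3.10.1, the bullet on unacceptable toxicity refers to 3.3, but the 4-week bullet does not.

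**The case against.** The strongest defense is that the tables cover different times. Section 3.3.1 assigns Table 11 to changes during a cycle and Table 8 to the start of a cycle, while 3.3.1.1 concerns day 1. The temozolomide rules could then run in sequence: late recovery before the day 1 delay is used up means resuming lower, and no recovery by then means stopping. For the two hold-until-resolved cells this reading is available, and it stands as long as the clock is undefined. It does not explain why 3.3.1.1 cites Table 11 as its summary. Nor does it separate the tables fully: for d of 2 or more, d + 28 is at least 30, so any mid-cycle hold longer than 4 weeks passes day 29 and also meets Table 8. It does not help Table 8's zotiraciclib cell, which is itself a start-of-cycle rule and reduces when the event is unresolved.

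A second defense is intent. Every grade 3 cell with a 4-week outcome stops and every reducing cell is grade 2, so reduction for grade 2 may be deliberate. That is plausible, but then 3.3.1.1 and 3.10.1 are the texts that need changing.

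Third, the practical effect is limited. The principal investigator reviews each patient's adverse events (7.4.1), and 13.1.5 reports average count recovery within two weeks of nadir in a temozolomide study. This bears on frequency and does not remove the contradiction.

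A reader might infer that the protocol directs temozolomide to be given again while neutrophils or platelets are still grade 2. The documents do not support that: the temozolomide cell opens with a hold until grade 1 or less. A reader might also count the third temozolomide de-escalation, where 3.3.1.2 stops only temozolomide and 3.10.1 ends protocol therapy. That is an ambiguity, because 3.3.1 only permits zotiraciclib to continue and can be read as yielding to 3.10.1. It is not part of this point, and neither is the reference in 3.3.1.2 to table 10 for a dose level that is in Table 9.

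**Conclusion.** The inconsistency is real and should be corrected. For a treatment-related grade 2 event unresolved after 4 weeks:

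- Table 8's zotiraciclib non-hematologic cell and Table 11's zotiraciclib hematologic cell conflict with 3.10.1.
- Table 11's zotiraciclib non-hematologic and temozolomide hematologic cells conflict with it if the rest period runs from the first held dose, even when they are read as resuming lower after late recovery.
- The temozolomide cell also does not match 3.3.1.1 or Table 8's hematologic row.

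The 3.10.1 conflicts require the event to be treatment-related. The number of patients affected cannot be computed, because the documents give no rate of holds longer than 4 weeks; it is probably small. The 14-day gap in the example illustrates the undefined clock under a fixed day 1 and is not an effect size. No bias in progression-free survival is claimed.

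**What to change.** State once in 3.3 that the 4 weeks run from the first held dose. Section 3.1.3 can keep its own start point for DLT. Then make the text give one answer, by one of two routes:

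- **Stop.** Change the four grade 2 cells so that a treatment-related event unresolved at 4 weeks stops the drug, in line with 3.3.1.1, 3.10.1 and Table 8's hematologic row. The downside is that a slow-recovering grade 2 patient loses the reduced-dose option.
- **Reduce.** If reduction was intended for grade 2, exempt grade 2 explicitly in 3.3.1.1, 3.10.1 and Table 8's hematologic row, and require recovery to grade 1 or less before re-dosing. This route should also say what happens to a patient already on 150 mg zotiraciclib, since Table 10 has no lower level.

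On either route, reword the 3.3.2 sentence that keeps the zotiraciclib dose unchanged below grade 3. The cost is a protocol amendment. No patients, visits or data fields are added.
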